#### **Secondary Analyses**

The year 2 secondary efficacy endpoints include: Qmax; prostate volume; IPSS improvement of  $\geq 2$  points,  $\geq 3$  points and, separately,  $\geq 25\%$  improvement from baseline; and Qmax improvement of  $\geq 3$ ml/sec and, separately,  $\geq 30\%$  improvement from baseline. Time to AUR or BPH-related surgical intervention is also a secondary efficacy endpoint.

The following describes the year 2 secondary efficacy endpoints and associated analyses. All treatment comparisons referenced are in terms of the combination therapy versus 0.2 mg tamsulosin.

 Prostate volume, change from baseline prostate volume, and percentage change from baseline prostate volume will be summarized by treatment group using both the LOCF and At Visit approaches at each scheduled post-baseline assessment.
 Percentage change from baseline prostate volume will be compared at each scheduled post-baseline assessment using the following general linear model:

log(post-baseline prostate volume/baseline prostate volume) = log(baseline prostate volume) + treatment + cluster

- Symptom improvement is measured using the IPSS and also evaluated using a categorical change from baseline improvement of ≥2 points and ≥3 points and, separately, ≥25% improvement from baseline. Treatment comparisons will utilise a Mantel-Haenszel test controlling for cluster at alpha=0.05.
- Maximum urinary flow (Qmax), change from baseline Qmax, and percentage change from baseline Qmax will be summarized by treatment group using both the LOCF and At Visit approaches at each scheduled post-baseline assessment. Change from baseline Qmax will be compared at each scheduled post-baseline assessment using a general linear model with effects for treatment, cluster, and baseline Qmax.
- Qmax improvement of ≥3mL/sec and, separately, ≥30% improvement from baseline will be computed by treatment group. Treatment comparisons will utilise a Mantel-Haenszel test controlling for cluster at alpha=0.05.
- Time to first AUR or BPH-related surgical intervention will be defined as the number of days from date of first dose of randomized study drug to date of the first event (earliest occurring of either AUR or BPH-related surgery) for each subject. Censoring will occur at the earliest of the following dates as applicable: the date of prostatectomy, the date of last contact for AUR and surgical intervention assessment,

and the date of death. As an additional summary the number of subjects having the first AUR or BPH-related surgery event on or after first dose of study drug will be tabulated by treatment and by annual time period along with the number of subjects at risk during each of these time periods. Treatments will be compared in terms of time to first AUR or BPH-related surgery for the ITT population using a log rank test at the 0.05 level of significance.

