#### 7.2.1.1. Secondary Endpoints

The secondary efficacy endpoints of this study are:

- Percent change in prostate volume from baseline
- Proportion of subjects with IPSS improvement of  $\geq 2$  points and  $\geq 3$  points from baseline and, separately,  $\geq 25\%$  improvement from baseline
- Change in Qmax from baseline
- Proportion of subjects with Qmax improvement of ≥3mL/sec and, separately, ≥30% improvement from baseline
- Time to event/proportion of subjects with AUR or BPH related prostatic surgery
- Time to event/proportion of subjects with AUR
- Time to event/proportion of subjects undergoing BPH related prostatic surgery

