## 9.3.7.1. Efficacy Analyses

#### **Primary Analysis**

The primary efficacy parameter after two years of study treatment is change from baseline IPSS. Symptom improvement is measured using the IPSS and evaluated using change from baseline.

Total IPSS, change from baseline IPSS, and percentage change from baseline IPSS will be summarized by treatment group using both the LOCF and At Visit approaches at each scheduled post-baseline assessment. Change in baseline IPSS will be compared at each scheduled post-baseline assessment for combination therapy versus 0.2mg tamsulosin using a general linear model with effects for treatment, cluster, and baseline IPSS at alpha=0.05.

CONFIDENTIAL

Missing individual responses for the IPSS questionnaire will be imputed as defined in Section 9.3.7.

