#### 9.3.7.2.1. Other Safety Measures

#### Serum PSA

Total PSA, change from baseline total PSA, and percentage change from baseline total PSA will be summarized by treatment group using both the LOCF and At Visit approaches at each scheduled post-baseline assessment.

Change from baseline total PSA will be compared at each scheduled post-baseline assessment using a general linear model with effects for treatment and baseline total PSA. Statistical analysis of the change from baseline total PSA comparing the treatment groups will begin using data from the final scheduled assessment. Abnormalities at any assessment will be listed by treatment and subject.

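### IPSS and Qmax responder tests adjust for cluster only, although the continuous analysis of the same variable also adjusts for baseline: a modest, avoidable loss of power

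*Protocol*

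**What the plan says.** Protocol Section 9.3.7.1, Secondary Analyses, names the test for both groups of responder endpoints.

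- **IPSS responders** (at least 2 points, at least 3 points and, separately, at least 25%): "Treatment comparisons will utilise a Mantel-Haenszel test controlling for cluster at alpha=0.05".
- **Qmax responders**: the text says "Qmax improvement of ≥3mL/sec and, separately, ≥30% improvement from baseline will be computed by treatment group", and the same Mantel-Haenszel sentence follows.

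The continuous analyses of the same two measures carry one more term.

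- **IPSS change** (Primary Analysis): "general linear model with effects for treatment, cluster, and baseline IPSS at alpha=0.05".
- **Qmax change** (Secondary Analyses): "general linear model with effects for treatment, cluster, and baseline Qmax".

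Section 9.3.7 leaves complete details to the Reporting and Analysis Plan (RAP), where deviations and additions are also to be documented. The RAP was not available. The responder test, its control variable and its alpha are nevertheless fixed in the protocol itself, so this is a stated method and not a gap left for later.

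**The concern.** Whether a man counts as a responder can depend on where he started. Section 4.1.2 admits a Qmax above 5 and up to 15 mL/sec at screening, so a 30% response means anything from about 0.30 × 5 = 1.5 to 0.30 × 15 = 4.5 mL/sec. Entry IPSS has a floor of 12 and no stated ceiling, so men with high scores have more room to fall by 2 or 3 points. Defining response as change from baseline does not remove this dependence.

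The protocol treats baseline as worth adjusting for when IPSS and Qmax are continuous, and drops it, without a reason, when the same variables are dichotomised. If baseline predicts response, the responder tests have less power than the collected data allow. They are also not aligned with the continuous analysis beside which they will be read.

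**Working it through.** **1. The plan's own figure.** Section 9.2.1 gives a difference of 1.8, SD 6, 90% power and (Section 9.1) two-sided 0.05:

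n per arm = 2 × (1.960 + 1.282)² × 6² / 1.8² = 233.5, so 234. With 20% discontinuation, 234 / 0.80 = 292.5, so 293.

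Power with 234 per arm is 82.2%, 90.1% and 95.0% for differences of 1.6, 1.8 and 2.0, against 82%, 90% and 95% in Section 9.2.2. These figures reproduce and this point does not affect them. The protocol states no power for the responder endpoints.

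**2. Simulation of the IPSS responders.** From the protocol: difference 1.8, SD of change 6, 293 per arm, 1:1. Not in the protocol, hence assumed: baseline IPSS mean 18 and SD 6, control mean change −5, 10 clusters with no cluster effect, every randomised man contributing, and correlation r between baseline and improvement from 0 to 0.6. There were 1,500 trials per row. Each cell shows power of Mantel-Haenszel by cluster → logistic regression with treatment, cluster and baseline. Gains were taken before rounding.

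| r | ≥2 points | ≥3 points | ≥25% |
|---|---|---|---|
| 0 | 73.3 → 73.9 (+0.6) | 74.9 → 75.4 (+0.5) | 78.7 → 80.1 (+1.3) |
| 0.3 | 73.2 → 75.9 (+2.7) | 78.7 → 81.1 (+2.4) | 83.5 → 83.8 (+0.3) |
| 0.5 | 75.5 → 80.7 (+5.3) | 78.9 → 84.7 (+5.9) | 88.5 → 89.7 (+1.2) |
| 0.6 | 74.5 → 84.4 (+9.9) | 76.2 → 85.4 (+9.2) | 90.7 → 93.5 (+2.8) |

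Monte Carlo error on a single power is about √(0.75 × 0.25 / 1500) = 1.1 points. Both tests were run on the same simulated trials, so the error of a difference is smaller.

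**3. Second set of assumptions.** Baseline mean 16, SD 6, 8 clusters, slope of change on baseline −0.3 or −0.5:

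- Slope −0.3: ≥2 points 76.5 → 79.1 (+2.6); ≥3 points 77.4 → 80.4 (+3.0); ≥25% 82.6 → 82.8 (+0.2).
- Slope −0.5: ≥2 points 75.5 → 82.7 (+7.2); ≥3 points 79.4 → 86.3 (+6.9); ≥25% 89.2 → 90.7 (+1.5).

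**4. Which rows apply.** r = slope × baseline SD / SD of change. With SD 6 and slopes 0.3 and 0.5, r = 0.3 and 0.5. With SD 4, r = 0.3 × 4 / 6 = 0.20 and 0.5 × 4 / 6 = 0.33. A narrower baseline therefore moves the gain down to the r = 0.3 row or a little below it, but not to nil.

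**5. The gain in subjects.** The equivalent ratio is [(1.960 + z_new) / (1.960 + z_old)]², where z is the normal quantile of the power. For ≥2 points:

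- Slope −0.5: [(1.960 + 0.942) / (1.960 + 0.690)]² = 1.20.
- Slope −0.3: [(1.960 + 0.810) / (1.960 + 0.722)]² = 1.07.

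So adjustment is worth about 7% to 20% more subjects for that endpoint under these assumptions.

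**6. Validity.** With no treatment effect, r = 0.5 and 2,500 trials, the planned test rejects in 4.9% (≥3 points) and 5.5% (≥25%). The logistic test rejects in 4.6% and 5.7%. Monte Carlo error is √(0.05 × 0.95 / 2500) = 0.4 points, so both are nominal.

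**7. Qmax.** No calculation is possible without assuming both a Qmax SD and a Qmax effect, since the protocol gives neither.

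**The case against.** The strongest reply is that nothing here is wrong. A cluster-stratified Mantel-Haenszel test is a standard prespecified test for a binary endpoint, and its type I error is nominal. That stands.

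Three stronger readings are tempting, and the documents do not support them.

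- **Bias.** A reader might infer that the responder results are biased, or that chance baseline imbalance is an uncorrected fault. Under 1:1 randomisation the nominal error rate already covers chance imbalance. How often the responder and continuous results would disagree because of it has not been measured.
- **Baseline IPSS and Qmax used throughout.** A reader might infer that every continuous model includes these two baselines. Each enters only the model of its own variable. Prostate volume is modelled on "log(baseline prostate volume) + treatment + cluster" and PSA by a "general linear model with effects for treatment and baseline total PSA". BHS, BII and PAS-SFI each use their own baseline. Post-void residual volume (Section 9.3.7.2.1) is compared by a van Elteren test on cluster with no baseline term, so cluster-only control is not confined to the responder endpoints.
- **All five endpoints shown to lose power.** The calculation covers only the three IPSS responders, and the 25% responder barely moves. The 1.5 to 4.5 mL/sec illustration uses the screening range, not the Visit 2 baseline, and does not by itself show that Qmax response depends on baseline.

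The baseline assumptions can also be challenged. A normal baseline with mean 16 and SD 6 puts about 25% of men below 12, although IPSS of at least 12 is required at pre-screening. Scores may fall below 12 by Visit 2, but the true SD may well be less than 6. This lowers the gain without removing it. At r = 0 the gain is essentially nil, and adjustment costs no power either.

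Finally, the RAP could add a covariate-adjusted responder analysis. That is possible, but the protocol's named test would remain the main one unless changed.

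**Conclusion.** The point holds as an efficiency matter. The responder tests control for cluster only, while the continuous analysis of the same variable also adjusts for its baseline. With the protocol's difference of 1.8, SD 6 and 293 per arm, and assumed baseline SD 4 to 6 and slope 0.3 to 0.5, adding baseline is worth roughly 2 to 7 percentage points of power for the 2- and 3-point IPSS responders. The weakest corner (SD 4, slope 0.3) sits at or slightly under the bottom of that range. The 25% responder gains 0 to 2 points. The gains of 9 to 10 points at r = 0.6 lie outside these assumptions and should not be quoted as expected. The Qmax gain is unknown.

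The planned test is valid. The primary analysis, the sample size and the alpha level are unaffected. This is a worthwhile improvement to secondary endpoints, not the correction of an error.

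**What to change.** In Section 9.3.7.1, or in the RAP as a documented change, test each responder endpoint by logistic regression on treatment, cluster and the corresponding baseline value: baseline IPSS for the three IPSS responders and baseline Qmax for the two Qmax responders. Report the standardised risk difference with its 95% CI. Keep the cluster-stratified Mantel-Haenszel test as a supportive analysis.

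The cost is wording and programming only. Table 1 already schedules IPSS and Qmax at Visit 2, so no new data are needed. The downside is that the test becomes model-based and its odds ratio is conditional on baseline and cluster. The model test and the risk-difference interval may therefore occasionally disagree, so the plan should say in advance which of them decides. The change should be made before unblinding.

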## 5.4. Treatment Assignment

Subjects will be identified by a unique subject number that will remain consistent for the duration of the study.

Upon completion of all the required screening assessments, eligible subjects will be registered into RAMOS (Registration and Medication Ordering System), the GSK interactive voice response system (IVRS), by the investigator or authorized site staff.

Subjects will be randomized by investigative site using a randomization schedule generated by the GSK Biostatistical Department, which will assign subjects in a 1:1 ratio to either dutasteride 0.5mg + tamsulosin 0.2mg or placebo + tamsulosin 0.2mg. Once a randomization number has been assigned it must not be re-assigned even in cases of errors.

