## 9. DATA ANALYSIS AND STATISTICAL CONSIDERATIONS

## 9.1. Hypotheses

The primary endpoint is change from baseline IPSS. Let the following represent the mean change from baseline IPSS for each treatment group:

Hdut+tam: combination (0.5mg dutasteride and 0.2mg tamsulosin) treatment group

Htam: 0.2mg tamsulosin treatment group

Then the primary null and alternative hypotheses to be tested at Year 2 are as follows:

Description	Null Hypothesis	Alternative Hypothesis
Combination versus 0.2mg tamsulosin	H dut+tam = H tam	H dut+tam ≠ H tam

Two-sided tests of the null hypothesis will be conducted at the 0.05 level of significance to show superiority of the combination treatment group compared to 0.2mg tamsulosin at 2 years of treatment.

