## 9.2. Study Design Considerations

## 9.2.1. Sample Size Assumptions

The sample size was calculated based on estimates of IPSS change from baseline using information obtained from the CombAT study. Sample size estimates were computed in terms of a continuous response variable assuming a normal distribution, IPSS change from baseline mean difference between treatment groups of 1.8, a standard deviation of 6, and considering 90% power. With these assumptions, the required minimum sample size is 234 subjects per arm. Therefore, since a 20% treatment phase discontinuation rate is assumed, then randomization of 293 subjects per treatment arm (586 total) is required for 90% power.

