## 9.3.7. Key Elements of Analysis Plan

Data will be listed and summarized according to the GSK reporting standards, where applicable. Complete details will be documented in the RAP. Any deviations from, or additions to, the original analysis plan described in this protocol will be documented in the RAP and final study report.

As it is anticipated that accrual will be spread thinly across centers and summaries of data by center would be unlikely to be informative, data from all participating centers will be pooled prior to analysis. Investigative centers will be pooled a priori into clusters based on geographic location; these clusters may be used in analyses to adjust for site effects. Clusters will be defined once all investigative sites have been identified and randomisation has been completed.

All data up to the time of study completion/withdrawal from study will be included in the analysis, regardless of duration of treatment.

Analyses will be performed as appropriate using the LOCF along with the At Visit approach or the observed-cases approach and which will be assigned in subsequent sections. Missing individual responses for the IPSS questionnaire will be imputed when at least four of the seven questions are answered (non-missing). Missing individual responses for the BII questionnaire will be imputed when at least two of the four questions are answered (non-missing). For the imputation, the average of the non-missing responses will be calculated and rounded to the nearest integer. This average score will be imputed for the original missing response(s). If at least 20% of the subjects have at least one imputed score for either IPSS or BII then that questionnaire's statistical analyses will be repeated based on non-imputed scores.

For purposes of data analyses, the baseline value of a particular type of assessment for a given subject will be defined as the last assessment prior to the start of randomized treatment. Change from baseline for each subject will be computed as post-baseline value minus baseline value. Endpoints will be log-transformed where this will improve the assumptions underlying the analyses. Endpoints with log-transformations performed within the analysis model include prostate volume.

Demographic and baseline characteristics will be summarized.

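### The log-rank test for AUR or BPH-related surgery and the PSA model leave out the geographic cluster that the plan's other efficacy tests and linear models use; both are valid, but may lose a little power

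*Protocol*

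**What the plan says.** Section 5.4 states: "Subjects will be randomized by investigative site using a randomization schedule generated by the GSK Biostatistical Department", in a 1:1 ratio. It mentions neither a block size nor stratification.

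Section 9.3.7 adds: "Investigative centers will be pooled a priori into clusters based on geographic location; these clusters may be used in analyses to adjust for site effects". The clusters are to be defined after all sites are known and randomisation is complete.

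The comparisons described in the analysis sections treat cluster as follows.

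| Comparison | Section | Cluster used? |
|---|---|---|
| IPSS change (primary) | 9.3.7.1 | yes, linear model |
| Prostate volume, Qmax change | 9.3.7.1 | yes, linear models |
| IPSS and Qmax responders | 9.3.7.1 | yes: "Treatment comparisons will utilise a Mantel-Haenszel test controlling for cluster at alpha=0.05" |
| BHS, BII, PAS-SFI change | 9.3.7.3 | yes, linear models |
| Post-void residual volume | 9.3.7.2.1 | yes, van Elteren test |
| Time to first AUR or BPH-related surgery | 9.3.7.1 | **no** |
| Total PSA change | 9.3.7.2.1 | **no** |
| Adverse events, breast examination, abnormal changes in vital signs and DRE | 9.3.7.2 and 9.3.7.2.1 | no, Fisher's exact tests |

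On the time-to-event endpoint the text reads "Treatments will be compared in terms of time to first AUR or BPH-related surgery for the ITT population using a log rank test at the" (the sentence closes with a 5% significance level and names no strata). On PSA it reads "Change from baseline total PSA will be compared at each scheduled post-baseline assessment using a general linear model with effects for treatment and baseline total" (the covariate is the baseline value of the marker, and cluster is not among the effects).

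**The concern.** If allocation is balanced within sites, and so roughly within pools of sites, differences between clusters largely cancel out of the treatment contrast. A test that ignores cluster still counts those differences in its variance. When cluster predicts the outcome, the standard error is then a little too large, the actual type I error falls a little below nominal, and some power is lost.

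For most endpoints the plan avoids this by adjusting. It does not for AUR or BPH-related surgery, the only outcome that section 2.2.1 names, and it gives no reason. Prostatic surgery could plausibly vary with regional practice, although the protocol says nothing on this. With 586 men followed for 2 years the event count may be low, so power given up without need is worth recovering.

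**Working it through.** **1. The plan's own figures.** Section 9.1 says "Two-sided tests of the null hypothesis will be conducted at the 0.05 level of significance"; section 9.2.1 assumes "IPSS change from baseline mean difference between treatment groups of 1.8, a standard deviation of 6, and considering 90% power" and concludes that "the required minimum sample size is 234 subjects per arm".

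- n per arm = 2 × (1.960 + 1.282)² × 6² / 1.8² = 233.5, so 234.
- With 20% discontinuation: 234 / 0.80 = 292.5, so 293 per arm and 586 in total.
- Power at 234 per arm for differences of 1.6, 1.8 and 2.0: 82.2%, 90.1% and 95.0%, against 82%, 90% and 95% in section 9.2.2.

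These figures reproduce. They concern IPSS, whose model includes cluster, so this point does not touch them. The protocol gives no event rate, hazard ratio or power for the log-rank or PSA comparison.

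**2. The two log-rank statistics.** At each event let g be 1 for a man on combination and 0 otherwise, and p the share of men at risk who are on combination. Then z = Σ(g − p) / √Σp(1 − p). The plain test takes p over all men at risk. The stratified test takes p within the man's cluster and adds both sums over clusters.

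**3. Simulation with site-blocked allocation.** Assumed, since the protocol does not give them: 586 men, 40 sites, blocks of 4 within site, 8 clusters, exponential event times, 2-year follow-up with about 10% random loss, and hazard ratio 0.4 for power. There were 4,000 null runs (simulation standard error √(0.05 × 0.95 / 4000) = 0.0034) and 2,000 power runs.

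| Control 2-year rate | Between-cluster SD of log hazard | Type I: plain / stratified | Power: plain / stratified |
|---|---|---|---|
| 3% | 0 | 0.048 / 0.049 | 30.2% / 30.4% |
| 3% | 0.5 | 0.047 / 0.049 | 29.8% / 30.7% |
| 3% | 1.0 | 0.039 / 0.041 | 27.7% / 28.7% |
| 5% | 0 | 0.048 / 0.047 | 48.4% / 48.5% |
| 5% | 0.5 | 0.046 / 0.045 | 47.3% / 47.4% |
| 5% | 1.0 | 0.045 / 0.046 | 42.6% / 43.6% |
| 10% | 0 | 0.047 / 0.047 | 78.7% / 78.6% |
| 10% | 0.5 | 0.049 / 0.049 | 77.4% / 77.7% |
| 10% | 1.0 | 0.050 / 0.055 | 71.0% / 72.6% |

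Stratifying changes power by −0.1 to +0.2 points at SD 0, by +0.1 to +0.9 at SD 0.5, and by +1.0 to +1.6 at SD 1.0. At this precision the type I errors of the two tests cannot be told apart.

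**4. Simulation with exact balance within clusters.** Assumed: 8 clusters of 74 men, 1:1 within each, censoring at 2 years, hazard ratio 0.4. The two unequal scenarios used 20,000 runs (standard error about 0.0015 near 0.05), the equal one 4,000.

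| Control rates across clusters | Type I: plain / stratified | Power: plain / stratified |
|---|---|---|
| 6% in all | not run | 59.5% / 59.6% |
| 1% to 15% | 0.046 / 0.050 | 65.0% / 66.0% |
| half 1%, half 20% | 0.038 / 0.048 | 82.0% / 83.8% |

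The gains are 0.1, 1.0 and 1.8 points. Conservatism is plain only in the last, deliberately extreme, scenario.

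**5. PSA-type linear model.** Same 40 sites, blocks and 8 clusters; 4,000 null runs; the share of residual variance lying between clusters (ICC) is assumed.

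| ICC | Type I without cluster | Type I with cluster |
|---|---|---|
| 0 | 0.046 | 0.048 |
| 0.02 | 0.046 | 0.048 |
| 0.05 | 0.051 | 0.054 |
| 0.10 | 0.041 | 0.049 |
| 0.20 | 0.034 | 0.048 |

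The effect shows only from an ICC of about 0.10 upwards.

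**The case against.** **An unstratified log-rank test is standard and valid, and the loss is tiny.** This stands. It limits the point to an optional improvement.

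**The details belong to the Reporting and Analysis Plan, and section 9.3.7 says only that clusters may be used.** This stands in part: the permissive wording means that an unadjusted test contradicts no rule. But the protocol does not leave these two methods open. It names a test or model for each endpoint, states the cluster adjustment nearly every time, and here fixes a version without it.

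**Cluster is not the randomisation unit.** This stands. Allocation is by site, clusters are coarser pools formed afterwards, and no blocking is stated. A reader might infer that these two analyses ignore the randomisation grouping while the others respect it. The documents do not support so clean a split, because the cluster-adjusted analyses reflect site only in part.

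**PSA is a safety measure, and other safety tests omit cluster too.** This is correct: the Fisher's exact comparisons do. A reader might infer that only two comparisons in the whole plan lack cluster, which is wrong. The claim is limited to the efficacy and health-outcome comparisons and, for PSA, to the general linear models.

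**The outcome is less central than section 2.2.1 suggests.** The Protocol Summary words the secondary objective more broadly, and section 7.2.1.1 lists several secondary endpoints. This is fair, and it is a further reason to rate the point low.

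**Conclusion.** The inconsistency is in the text. The log-rank test for AUR or BPH-related surgery is the only efficacy or health-outcome comparison described without cluster, and the PSA model is the only general linear model without it.

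The consequence is conditional and small. If clusters differ strongly in event risk, the log-rank test gives up about 1 to 2 power points; if they do not differ, it gives up nothing detectable. The PSA model becomes noticeably conservative only if a sizeable share of the variance lies between clusters. These sizes rest on assumed event rates, hazard ratio, cluster numbers and between-cluster variation, none of which the protocol supplies.

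Two stronger readings should be resisted. One is that the log-rank test is conservative as a matter of fact: that needs between-cluster differences which the protocol does not quantify. The other is that the result would be invalid or the trial undersized: leaving out a prognostic grouping factor does not inflate false positives here, and the sample size rests on IPSS. This is a minor point and a free improvement.

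**What to change.** - Section 9.3.7.1, time to first AUR or BPH-related surgery: specify *a log rank test stratified by cluster*.
- Section 9.3.7.2.1, Serum PSA: specify a linear model with *effects for treatment, cluster, and baseline total PSA*.

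Leave the general statement in section 9.3.7 that clusters may be used, and leave the Fisher's exact safety tests as they are. Making cluster adjustment compulsory throughout would conflict with those tests. If the sponsor prefers the unstratified log-rank test, for instance because events per cluster will be few, one sentence giving that reason would also settle the matter.

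The cost is a few words. No new data are needed, since the clusters are already required for the primary model. The only downside is a negligible loss of information if some clusters are very small, because an event adds nothing to the stratified test when all men at risk in its cluster are in one arm.
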